1. SYNOPSIS

Protocol Title: A randomized, open-label, cross-over, placebo-device study investigating critical and over all errors, training/teaching time, and preference attributes of the ELLIPTA dry powder Inhaler (DPI) as compared to HandiHaler DPI used in combination with either DISKUS DPI or Turbuhaler DPI, in adult patients with Chronic Obstructive Pulmonary Disease (COPD)

Short Title: A clinical study assessing critical errors, training/teaching time, and preference attributes of the ELLIPTA dry powder inhaler, in comparison to combinations of dry powder inhalers used to provide triple therapy, in patients with COPD.

Rationale: This study is designed to assess the benefits of delivering triple therapy using a single ELLIPTA™ DPI (Closed Triple therapy) *versus* delivering triple therapy using two different types of inhalers (open triple therapy) to patients with Chronic Obstructive Pulmonary Disease (COPD). It will assess the proportion of COPD subjects who make critical errors when using a single ELLIPTA™ DPI *versus* those using combinations of commercially available and commonly used DPIs: DISKUS used in combination with HandiHaler, or Turbuhaler used in combination with HandiHaler. This study would also assess training/teaching time and preference attributes for closed triple therapy as compared to the open triple therapy.

Objectives and Endpoints:

Objectives	Endpoints
Primary	
To compare the number of critical errors made by COPD patients, after a subject has read the respective patient information leaflet(s) (PIL), for each treatment option tested	
 The percentage of subjects making at least one critical error after reading the PIL(s)
Secondary	
To compare the number of critical errors made by COPD patients after instruction from the Healthcare Professional (HCP) for each treatment option tested	The percentage of subjects making at least one critical error after the: 
 first instruction from the HCP second instruction from the HCP
To compare the number of overall (critical and non-critical) errors made by COPD patients, after a subject has read the PIL(S) or after Instruction from the HCP for each treatment option tested	
 The percentage of subjects making at least one overall error after reading the PIL(s) The percentage of subjects making at least one overall error after the first instruction from the HCP The percentage of subjects making at least one overall error after the second instruction from the HCP

Objectives	Endpoints
To compare the number of instructions (maximum of 2) from a HCP which is needed to demonstrate correct inhaler use	The number of instructions (0, 1 or 2 times) from the HCP which are needed to demonstrate correct inhaler use
To compare the Training/Teaching Time required to demonstrate correct inhaler use	
 • The total amount of time taken to demonstrate correct inhaler use (T1+T2). • The amount of time taken to read the patient information leaflet and demonstrate correct inhaler use (T1) • The amount of time taken to be given instruction by the HCP (up to 2 times) on use of the inhaler and to demonstrate correct inhaler use (T2)
Preference attributes for each treatment option tested	Treatment preference, from questionnaire for: 
 • Number of steps required to take COPD medication • Over all treatment preference

Overall Design: The study will be conducted as a multi-centre, randomized, open-label, placebo-device, cross-over study, with a 2x2 complete block design.

[figure not shown]
It will comprise of two sub-studies:

- Sub-study 1: Will compare ELLIPTA DPI to DISKUS-HandiHaler DPI combination
- Sub-study 2: Will compare ELLIPTA DPI to Turbuhaler-HandiHaler DPI combination.

The study has 2 visits (V0 and V1) and both can be completed on the same day.

Each sub-study may run independently or in parallel of the other sub study. Each will start dependent on the availability of the placebo DPIs required for that sub-study. The data from the 2 sub studies may be reported independently and as each sub study completes.

Study Schematic

Number of Participants: Sufficient patients with COPD will be screened to ensure approximately 160 participants will be randomized, such that approximately 144 evaluable participants complete the study. Approximately 72 participants completing in each sub study.

Treatment Groups and Duration: Duration is a single visit and subjects are randomised to receive treatments below; dependent on which sub-study they are included in.

There is no active treatment and subjects will continue to take their own prescribed COPD medication for the duration of the study.

Sub Study 1 Treatment Sequences

Sequence	Period 1	Period 2	Preference Questionnaire
A	ELLIPTA	DISKUS + HandiHaler	1
B	DISKUS + HandiHaler	ELLIPTA	2
C	ELLIPTA	DISKUS + HandiHaler	2
D	DISKUS + HandiHaler	ELLIPTA	1

Sub Study 2 Treatment Sequence

Sequence	Period 1	Period 2	Preference Questionnaire
E	ELLIPTA	Turbuhaler + HandiHaler	3
F	Turbuhaler + HandiHaler	ELLIPTA	4
G	ELLIPTA	Turbuhaler + HandiHaler	4
H	Turbuhaler + HandiHaler	ELLIPTA	3

2. SCHEDULE OF ACTIVITIES (SOA)

Visit Number	V0	V1	Notes
Study Day	1	1	V0 can take place on the same day as V1. V1 should be completed no later than 30 days after consent.
Procedure:			
Screening Assessments			Completed prior to randomisation
Written informed consent	X		Informed consent may take place prior to V0 for logistical reasons. Subjects should be included and randomised within 30 days of providing consent.
Subject demography	X		Age, height, weight, year of birth, sex, ethnicity and geographic ancestry will be recorded
Medical/disease history including Chronic Obstructive Pulmonary Disease (COPD)	X		Subject will have a medical history of COPD, previously confirmed by spirometry.
Concomitant medication history including COPD Therapy History	X		Current concomitant medication will be recorded. A minimum COPD therapy history for the preceding 2 years from inclusion will be recorded
Inclusion/exclusion criteria	X		All criteria must be met prior to randomisation at V1
Study Assessments			Completed once a subject is included on study
Randomisation		X	Randomised to treatment order and preference questionnaire
Assess the number of inhaler errors (critical and overall) on each treatment after reading the Patient information leaflet (PIL) for Inhaler tested		X	No instruction is provided by the Health Care Professional (HCP) for this assessment.
Assess the number of inhaler errors (overall and critical) on each treatment after each of 2 attempts following instruction by HCP			If a subject cannot show correct use after reading the PIL, then the HCP has up to 2 attempts to instruct the subject to attain this.

Visit Number	V0	V1	Notes
Teaching-Training Time for each inhaler includes the following: 
 The amount of time taken to read the patient information leaflet and demonstrate inhaler use The amount of time taken to be given instruction by the HCP on use of the inhaler and demonstrate inhaler use The total amount of time taken to demonstrate inhaler use 		X	
 First assessment is attempt one, including time to read PIL and demonstrate use. Second assessment will be time for HCP to correct errors and subject to show use for up to 2 more attempts The Cumulative time for all assessments needed by subject and any HCP instruction to demonstrate no errors will also be captured.
Preference Questionnaire		X	Subject will complete version of Preference Questionnaire they have been randomised to.
SAE/AE assessment		X	Collected until completion of final study assessment at V1.

3. INTRODUCTION

3.1. Study Rationale

Please note that Turbohaler and ACCUHALER are the names commonly used within the United Kingdom for these inhalers. However, in other regions and for the purposes of this study these inhalers are referred to as Turbuhaler and DISKUS respectively in this protocol.

This study is designed to assess the benefits of delivering triple therapy using a single ELLIPTA™ Dry Powder Inhaler (DPI) (Closed Triple therapy) *versus* delivering triple therapy using two different types of inhalers (open triple therapy) to patients with COPD. It will assess the proportion of COPD subjects who make critical errors when using a single ELLIPTA DPI *versus* those using combinations of commercially available and commonly used DPIs: DISKUS used in combination with HandiHaler, or Turbuhaler used in combination with HandiHaler. This study would also assess training/teaching time and preference attributes for closed triple therapy as compared to the open triple therapy.

3.2. Background

Chronic Obstructive Pulmonary Disease (COPD) is a progressive disease of the airways. Noxious particles or gases lead to a modification in subject's airways which develop a chronic inflammatory response to these environmental factors. This leads to increasing airflow limitation, breathlessness and other symptoms. Despite being both treatable and preventable, COPD is a leading cause of morbidity and mortality worldwide. The economic and social burden of this disease has not been reduced and is increasing despite advances in diagnosis and treatment. [GOLD 2016]

The current treatment goals for COPD are to reduce and relieve symptoms and thereby improve exercise tolerance and health status, whilst reducing risk by preventing disease progression, preventing and treating exacerbations, and reducing mortality

Smoking cessation, inhaled pharmacological therapy, primarily long and short term bronchodilators (beta2-agonists and anti-cholinergics) and inhaled corticosteroids, and other non pharmacological interventions are currently used to achieve the treatment goals.

The current GOLD treatment guidelines, place patients in 4 groups from A to D, dependent on severity of symptoms and assessment of risk; with Group A patients having the fewest symptoms and a low risk as assessed by degree of airflow limitation and/or exacerbation history. COPD patients in Group A may just need a short acting bronchodilator as needed to relieve symptoms. However, as disease progresses, other inhaled therapies are added on to maintain control, such that COPD patients in Group D, who have many symptoms and a high risk of exacerbations and/or high airflow limitation, may need multiple inhaled therapies (inhaled corticosteroids (ICS), long-acting beta2-agonist (LABA) and long-acting anticholinergic (LAMA)).

Currently, subjects requiring triple therapy can be prescribed ICS/LABA and LAMA in separate inhalers. The specific ICS/LABA and LAMA prescribed determine whether the inhaler types (and thereby the inhalation techniques) and the dosing regimens are similar or different. Use of different inhaler types with different inhalation techniques and dosing regimens can add to treatment complexity, and also increase the potential for errors in inhaler use that reduce or preclude drug delivery to the site of action in the lungs [Cochrane, 2000, Van der Palen, 1999]. Fixed-dose combination inhalers that minimise the number of inhalers required would simplify treatment, improve adherence, reduce errors in inhaler use, and potentially lead to better outcomes [GOLD 2016].

The skill and ability of the COPD patient to use the prescribed inhaler/s correctly coupled with adequate training in inhaler technique are also critical to ensure effective drug delivery [Cochrane, 2000, Melani, 2011]. For any prescribed inhaler, the patient needs to follow all the steps in the patient leaflet correctly in order to ensure optimal drug delivery. In this regard, the time needed for a primary care nurse or physician, or a community pharmacist to train a patient in correct use of an inhaler at the time of initial prescription, and for any subsequent retraining becomes important. Given the time demands on healthcare professionals, a device which is simple to use and requires minimal time to train would be desirable [Bonini, 2015]. Further, patients may prefer easy-to-use inhalers having fewer steps to deliver drug; this has the potential to improve compliance and thereby impact outcomes.

ELLIPTA DPI has been designed to be simple for patients to use. In COPD patients' naïve to Ellipta and comparator inhalers, data has shown that patients make fewer critical and overall errors when using ELLIPTA as compared to other common DPIs tested [Van Der Palen, 2016(a)]. ELLIPTA DPI was also shown to be preferred by patients for a number of attributes, including number of steps and training time required to receive therapy [Van Der Palen, 2016(b), Van Der Palen, 2016(c), Komase, 2014]. ELLIPTA is already available to deliver a LABA/ICS combination (BREO ELLIPTA), LAMA

(INCRUSE ELLIPTA), and LAMA/LABA combination (ANORO ELLIPTA). Closed triple therapy (ICS/LAMA/LABA) is currently being assessed in clinical studies to deliver all 3 active treatments from a single ELLIPTA DPI.

3.3. Benefit/Risk Assessment

The study involves use of placebo inhalers (placebo ELLIPTA, placebo DISKUS, placebo Turbuhaler and placebo HandiHaler) that do not contain active treatments and subjects will continue to take their own prescribed COPD medication and other concomitant medication for the duration of the study.

The placebo inhalers and placebo capsules for HandiHaler contain the excipients lactose or lactose blended with magnesium stearate. Excipients of the study inhaler are noted in Section 7.1. Subjects with a known hypersensitivity to any of these or severe milk protein allergy that could contraindicate study participation are excluded from the study (Section 6). Subjects who meet the inclusion/exclusion criteria will continue their COPD treatment as prescribed by their healthcare provider during their participation in the study. Subjects should continue to follow up with their regular physician for their COPD healthcare during the study.

The study procedures include reading of the inhaler patient information leaflets and demonstration of inhaler use by the study subjects and instruction in correct-inhaler use by the site staff.

3.3.1. Risk Assessment

Potential Risk of Clinical Significance	Summary of Data/Rationale for Risk	Mitigation Strategy
Paradoxical bronchospasm, which may occur with an immediate increase in wheezing after inhaling.	As with other inhalation therapy, paradoxical bronchospasm may occur with an immediate increase in wheezing after dosing. From post-marketing data, paradoxical bronchospasm has been reported at a frequency of <1/10,000 including isolated reports.	This should be treated immediately with a fast and short acting inhaled bronchodilator. Investigators will be instructed to assess the subject's condition to determine their eligibility to continue in the study and the need for alternative therapy.
Allergic reaction due to hypersensitivity to placebo excipients.	The placebo inhalers and placebo capsules (for HandiHaler) contain the excipients lactose and lactose blended with magnesium stearate. There are known allergies to these ingredients.	Subjects with a known hypersensitivity to any of these, or severe milk protein allergy that could contraindicate study participation are excluded from the study (Section 6.2). If an allergic reaction occurs, it should be treated immediately with a fast and short acting inhaled bronchodilator. Investigators will be instructed to assess the subject's condition to determine their eligibility to continue in the study and the need for alternative therapy

3.3.2. Benefit Assessment

As this is a placebo study, no benefit to the subject is expected. No active treatment is being administered. The subjects will continue to receive their own COPD therapy as prescribed.

3.3.3. Overall Benefit: Risk Conclusion

The overall potential risk identified is minimal, due to the nature of the study.

4. OBJECTIVES AND ENDPOINTS

The study will compare critical errors, training time, and patient preference for closed triple therapy received from a single ELLIPTA inhaler *versus* open triple therapy received from HandiHaler in combination with either DISKUS or Turbuhaler. These comparisons will be performed as separate sub studies and the endpoints and objectives listed here will be the same for the treatment comparisons in each sub study:

- Sub study 1: ELLIPTA (Treatment option 1) versus the combination of DISKUS-HandiHaler (Treatment Option 2)
- Sub study 2: ELLIPTA ((Treatment option 1) versus the combination of Turbuhaler-HandiHaler (Treatment Option 3)

Objectives	Endpoints
Primary	
To compare the number of critical errors ^a made by COPD patients, after a subject has read the respective patient information leaflet(s) (PIL), for each treatment option tested	
 • The percentage of subjects making at least one critical error after reading the PIL(s)
Secondary	
To compare the number of critical errors made by COPD patients after instruction from the Healthcare Professional (HCP) for each treatment option tested	The percentage of subjects making at least one critical error after the: 
 • first instruction from the HCP • second instruction from the HCP ^d
To compare the number of overall ^a (critical and non-critical) errors made by COPD patients, after a subject has read the PIL(S) or after Instruction from the HCP for each treatment option tested	
 • The percentage of subjects making at least one overall error after reading the PIL(s) • The percentage of subjects making at least one overall error after the first instruction from the HCP • The percentage of subjects making at least one overall error after the second instruction from the HCP ^d

Objectives	Endpoints
To compare the number of instructions (maximum of 2) from a HCP which is needed to demonstrate correct inhaler use ^c	The number of instructions (0, 1 or 2 times) from the HCP which are needed to demonstrate correct inhaler use
To compare the Training/Teaching Time required to demonstrate correct inhaler use	
 • The total amount of time taken to demonstrate correct inhaler use (T1+T2). • The amount of time taken to read the patient information leaflet and demonstrate correct inhaler use (T1) ^d • The amount of time taken to be given instruction by the HCP (up to 2 times) on use of the inhaler and to demonstrate correct inhaler use (T2) ^d
Preference attributes for each treatment option tested ^b	Treatment preference, from questionnaire for: 
 • Number of steps required to take COPD medication • Over all treatment preference
a. Over all and critical errors for each inhaler tested, as well as an explanation of how these endpoints were defined, are listed in Appendix 2 b. Preference Questionnaires for each sub-study are included in Appendix 3 c. To show correct inhaler use a subject demonstrates the use of the inhaler without making any critical or non-critical error d. Endpoint will be treated as 'other endpoint' and not secondary for the statistical analysis	

5. STUDY DESIGN

5.1. Overall Design

The study will be conducted as a multi-centre, randomized, open-label, placebo-device, cross-over study, with a 2x2 complete block design.

It will comprise of two sub-studies:

[figure not shown]
- Sub-study 1: Will compare ELLIPTA DPI (Treatment option 1) to DISKUS-HandiHaler DPI combination (Treatment option 2)
- Sub-study 2: Will compare ELLIPTA DPI (Treatment option 1) to Turbuhaler-HandiHaler DPI combination (Treatment option 3).

The study has 2 visits (V0 and V1) and both can be completed on the same day.

Each sub-study may run independently or in parallel of the other sub study. Each will start dependent on the availability of the placebo DPIs required for that sub-study. The data from the 2 sub studies will be reported independently and as each sub study completes and the data have been cleaned. The database will be locked when all of the sub-studies have completed and data are cleaned.

The study subjects will be randomised to order of treatment and preference questionnaire in each of the 2 sub studies. This is shown in further detail in Figure 1.

Figure 1 Study Schematic

5.2. Number of Participants

Sufficient patients with COPD will be screened to ensure approximately 160 participants will be randomized, such that approximately 144 evaluable participants complete the study. An evaluable subject is defined in the intent to treat population in Section 10.3. Approximately 72 participants completing in each sub study.

If participants prematurely discontinue the study, additional replacement participants may be recruited at the discretion of the Sponsor.

5.3. Participant and Study Completion

A participant is considered to have completed the study if he/she has completed all phases of the study including the last scheduled procedure shown in the Schedule of Activities.

The end of the study is defined as the date of the last visit of the last participant in the study.

5.4. Scientific Rationale for Study Design

This design has been used in previous studies looking at critical errors and/or preference of inhalers in patients with COPD and naive to the inhalers tested. The cross-over design was chosen to allow the subjects to serve as their own control in their ability to use both the ELLIPTA DPI and the other combination DPIs. A single visit is suitable for assessing these endpoints and reduces inconvenience of multiple visits for subject included.

Placebo inhalers are used to remove any bias due to treatment effect, avoid the need for wash-in/-out periods, and to avoid the need to withhold or discontinue current COPD medications, which may affect the subject's clinical status (improvement or decline) and perceptions, as noted above.

5.5. Dose Justification

Not applicable as this is a placebo-only study.

6. STUDY POPULATION

Prospective approval of protocol deviations to recruitment and enrolment criteria, also known as protocol waivers or exemptions, is not permitted.

6.1. Inclusion Criteria

Participants are eligible to be included in the study only if all of the following criteria apply:

AGE
1. ≥ 40 years of age at Visit 1
TYPE OF SUBJECT AND DIAGNOSIS
2. Diagnosis of COPD with a documented history of COPD, in accordance with the definition by the European Respiratory Society [Celli, 2004].
3. Current COPD Therapy: Currently receiving maintenance therapy with a fixed dose combination of a long-acting beta 2-agonist (LABA) and inhaled corticosteroid (ICS). Subject may also be receiving long-acting muscarinic antagonist (LAMA; also known as a long-acting anti-cholinergic). Subjects must be able to continue using their currently prescribed COPD maintenance inhaler therapy throughout the study and as needed short acting beta-adrenergic agonist (SABA) and/or short acting muscarinic antagonist (SAMA) for rescue use.
4. Has been on current maintenance ICS/LABA COPD treatment for at least 4 weeks prior to V0 and evaluated as unlikely to change treatment within 4 weeks of Visit 1.
SMOKING HISTORY
5. Smoking History: Current or former (defined as subjects who have quit smoking for at least 3 months prior to V0/V1) cigarette smokers with a >10 pack-year smoking history [Number of pack years = (number of cigarettes per day \div 20) x number of

years smoked (e.g., 10 pack-years is equal to 20 cigarettes per day for 10 years, or 10 cigarettes per day for 20 years].
SEX
6. Males or Females who are not pregnant or not planning a pregnancy during the study or not lactating
INFORMED CONSENT
7. Capable of giving signed informed consent as described in Appendix 4 which includes compliance with the requirements and restrictions listed in the informed consent form (ICF) and in this protocol.

6.2. Exclusion Criteria

Participants are excluded from the study if any of the following criteria apply:

CONCURRENT CONDITIONS/MEDICAL HISTORY
1. Asthma: Subjects with a current diagnosis of asthma. Subjects with a prior history of asthma are eligible if they have a current diagnosis of COPD.
CONCOMITANT MEDICATIONS
2. Recent experience with the ELLIPTA inhaler: Subjects who used any ELLIPTA inhaler (e.g., RELVAR ELLIPTA, ANORO ELLIPTA, ARNUITY ELLIPTA, INCRUSE ELLIPTA, participated in a clinical study of GW685698, GW642444, GSK573719 [fluticasone furoate, vilanterol, umeclidinium bromide], or any combination thereof, or placebo in an ELLIPTA inhaler study) within 24 months prior to Visit 0.
3. Recent experience with any capsule inhaler: Subjects who used any capsule system inhaler (e.g. Spiriva HandiHaler, Seebri/Ultibro Breezhaler, or participated in a clinical studies of these, including placebo inhalers) within 24 months prior to Visit 0.
4. Dependent on which sub-study a subject is included on they should not have any recent experience, within 24 months of V0 of the following inhaler for the sub study included on: 
 • Sub Study 1: DISKUS inhaler (e.g. Seretide DISKUS or placebo DISKUS) • Sub Study 2: Turbuhaler (e.g. Symbicort Turbuhaler or placebo Turbuhaler)
RELEVANT HABITS
5. Drug/alcohol abuse: Subjects with a known or suspected alcohol or drug abuse at Visit 1 which in the opinion of the investigator could interfere with the subject's proper completion of the protocol requirement

CONTRAINDICATIONS
6. Drug/Food Allergy: A history of hypersensitivity to any components of the study inhaler (e.g., lactose, magnesium stearate). In addition, subjects with a history of severe milk protein allergy that, in the opinion of the study physician, contraindicates participation will also be excluded.
DIAGNOSTIC ASSESSMENTS AND OTHER CRITERIA
7. Investigational Product: Subjects who have received an investigational drug and/or medical device within 30 days of entry into this study (Screening/Visit 1), or within five drug half-lives of the investigational drug, whichever is longer
8. Inability to Read: In the opinion of the investigator, any subject who is unable to read and/or would not be able to complete a questionnaire and understand verbal instructions.

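### Device naivety is fixed at Visit 0 although devices are tested at Visit 1, so an add-on LAMA inhaler started between the visits is not clearly excluded

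*Protocol*

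**What the plan says.** Three criteria in Protocol 6.2 define device naivety. Exclusion 2 (ELLIPTA) applies to use "or placebo in an ELLIPTA inhaler study) within 24 months prior to Visit 0". Exclusion 3 (capsule inhalers) has the same anchor: "including placebo inhalers) within 24 months prior to Visit 0". Exclusion 4 (DISKUS or Turbuhaler, by sub-study) is worded differently: "they should not have any recent experience, within 24 months of V0 of the following inhaler for the sub study included on". Protocol 7.6 takes the inhaler history that informs inclusion from V0, going back 24 months.

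The devices are handled at V1. The Schedule of Activities says "V0 can take place on the same day as V1. V1 should be completed no later than 30 days after consent". It also allows consent before V0, ticks eligibility in the V0 column, and notes that every criterion must be satisfied before randomisation at V1.

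Two inclusion criteria in Protocol 6.1 bear on changes between the visits. Inclusion 3 requires that subjects can stay on their current maintenance inhaler therapy throughout the study, and it permits a LAMA in addition to ICS/LABA. Inclusion 4 begins "Has been on current maintenance ICS/LABA COPD treatment for at least 4 weeks prior to V0 and evaluated as unlikely to change treatment within 4" and goes on to tie that last period, in weeks, to Visit 1. Protocol 3.3 adds: "Subjects should continue to follow up with their regular physician for their COPD healthcare during the study".

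Protocol 5.4 rests the design on subjects new to the study devices, in a sentence that begins "This design has been used in previous studies looking at critical errors and/or preference of inhalers in patients with COPD and naive to the inhalers".

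**The concern.** The primary endpoint is the percentage of subjects making at least one critical error after reading the leaflet and before any instruction. It is meaningful only if the subject has not recently used the device. The naivety criteria stop at V0, so nothing in their wording for ELLIPTA or capsule inhalers covers the days from V0 to V1.

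An add-on LAMA is a foreseeable change in those days. Subjects may enter on ICS/LABA alone, Protocol 3.2 describes inhaled therapies being added as disease progresses, and routine COPD care continues. The same section names INCRUSE ELLIPTA as a LAMA product, and the open-triple option in both sub-studies is built by pairing HandiHaler with an ICS/LABA device. The added inhaler could therefore be one of the tested devices.

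Prior use would lower errors on one option only. A within-subject comparison does not cancel that. Exposure to a capsule device would shrink the contrast, and exposure to ELLIPTA would enlarge it.

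**Working it through.** **1. The plan's own figure.** Protocol 10.2 states at least 90% power with 72 subjects per sub-study, two-sided 5%, conditional logistic regression, for six error-rate pairs. Paired binary outcomes were simulated (4,000 runs per pair). Within-subject correlation is not stated, so zero was assumed. Treatment-only Wald power was 0.957, 0.949, 0.950, 0.936, 0.933 and 0.916 for the pairs from 11% v 37% down to 6% v 29%. The score test and the period-adjusted likelihood-ratio test gave 0.96 to 0.98. The stated figure reproduces on these assumptions. Wald power was lower in some settings (0.765 for 6% v 29% at an assumed correlation of 0.2; 0.57 to 0.82 with period adjustment at zero correlation, counting runs with an empty cell as non-significant). That reflects sparse discordant cells and does not depend on the naivety anchor.

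**2. Length of the gap.** V1 − V0 is at most 30 − (V0 − consent) days. It is 30 days at most, if V0 is the consent day, and 0 if the visits coincide.

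**3. Which criterion catches a change made in the gap.**

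| Change between V0 and V1 | Exclusions 2–4 | Inclusions 3 and 4 |
|---|---|---|
| ICS/LABA inhaler replaced by an ELLIPTA product | Not caught (exclusion 2 looks back from V0) | Conflicts with both |
| ICS/LABA inhaler replaced by DISKUS or Turbuhaler | Unclear (exclusion 4 can be read as covering both sides of V0) | Conflicts with both |
| LAMA added in ELLIPTA or a capsule device | Not caught (exclusions 2 and 3) | Inclusion 3 still met; inclusion 4 is a judgement that change is unlikely, and its stability requirement before V0 names ICS/LABA only |

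The last row is the open one. Checking all criteria before randomisation does not close it, because exclusions 2 and 3 give the same answer at V1 as at V0. Other criteria do reach V1: inclusion 1 and exclusion 5 are set at Visit 1, inclusion 5 at V0/V1, and exclusion 7 at Screening/Visit 1.

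**4. Size.** Inputs are n = 72 and the 10% v 35% pair from Protocol 10.2. The number of exposed subjects, k = 1 to 4 (1/72 = 1.4% to 4/72 = 5.6%), is an assumption. If exposed subjects make no critical error on that option, the expected rate is p × (72 − k)/72.

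- Comparator: 0.35 × 71/72 = 34.5% (k = 1); 0.35 × 68/72 = 33.1% (k = 4). The fall is 0.5 to 1.9 points.
- ELLIPTA: 0.10 × 71/72 = 9.9%; 0.10 × 68/72 = 9.4%. The fall is 0.1 to 0.6 points.

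The comparator figure is an upper bound, because a capsule device is only half of that option. Protocol 10.2 assumes that subjects who err do so on both devices. Under that assumption, mastering the HandiHaler leaves the error on DISKUS or Turbuhaler in place, and the option's rate moves by 0. The range is therefore 0 to 1.9 points against a planned difference of 35 − 10 = 25.

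**5. Effect on power.** At 11% v 37%, likelihood-ratio power is about 0.96 with no exposure. If 5% of subjects are exposed to the comparator, it is 0.96 (their error rate halved) to 0.94 (no errors). If 10% are exposed, it is 0.95 to 0.90. If 10% are exposed to ELLIPTA and make no ELLIPTA errors, it is 0.98.

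**The case against.** The strongest reply is that the inclusion criteria already protect the gap. A reader might infer from the V0 anchor that a subject switched to any of the four devices stays eligible. The documents do not support that. Replacing the ICS/LABA inhaler conflicts with inclusion 3, which runs throughout the study, and with inclusion 4, whose second part refers to Visit 1; both must hold before randomisation. Exclusion 4 may also cover time after V0. This part of the reply stands and removes the switching case.

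Inclusion 4 speaks of a change of treatment in general. A LAMA added on day 10 with testing on day 25 is 15 days from V1 and so inside the four weeks. An investigator could treat it as defeating the criterion. Another could read the criterion as concerning the ICS/LABA it names, or as a forecast properly made at V0. The add-on is therefore arguable rather than clearly excluded.

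A new inhaler would also be visible. Protocol 7.6 requires medication received during the study to be recorded with dates, and the SAP plans displays of COPD medications, protocol deviations and naivety to inhaler devices. This helps detection, but no rule links it to eligibility. SAP Section 4 defines no per-protocol population, and SAP 11.6.2 confines outlier exclusions to exploratory use, outside the primary analysis.

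Finally, the exposure is small: the protocol calls this a single-visit study, and the visits may coincide. That is right, and it limits the weight of the point.

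**Conclusion.** The point holds in a narrow form and is minor. Exclusions 2 and 3, exclusion 4 less clearly, and the 7.6 history fix naivety at V0, while the endpoint is measured at V1. The uncovered case is an add-on LAMA in an ELLIPTA or capsule device, started between visits held on different days.

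For an assumed 1 to 4 of 72 subjects at 10% v 35%, the shift is 0 to 1.9 points on the comparator, or at most about 0.6 points on ELLIPTA. These figures rest on assumed counts, since the documents give no rate of inhaler changes, and the upper ends assume that exposed subjects make no critical error on the whole option.

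Two stronger readings should not be drawn. One is that such a subject has just been taught the device: nothing in the documents says what instruction accompanies a new prescription, and prior use alone is enough for the point. The other is that the study is underpowered because of this. The planned sample size and power calculation are unaffected; what is at issue is whether every tested subject meets the naive, leaflet-only premise.

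**What to change.** In exclusions 2, 3 and 4, replace the V0 anchor with the 24 months before randomisation at Visit 1; this also removes the ambiguity in exclusion 4. Extend the device history in Protocol 7.6 to the same point. When V0 and V1 are on different days, have the site confirm, before contacting the IWRS, that the subject has used no ELLIPTA, capsule inhaler or sub-study comparator since V0.

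The cost is a wording change in three criteria and one history requirement, one question at V1, and an occasional extra screen failure. Sample size, significance level and analysis model stay as planned.
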